## **7 STATISTICAL CONSIDERATIONS**

### **7.1 Statistical Design and Sample Size Calculations**

Rationale: Assuming the SD of the PK parameters are approximately 50% of the mean of the PK parameters, which implies an effect size of two, a sample size of six analyzable patients will provide 95% confidence intervals with a margin of error, based on a t distribution with five degrees of freedom, of approximately +/- 52.5% of the mean. These are typical for PK estimation studies.

### **7.2 Study Objectives and End Points**

The endpoint of the study is the successful evaluation of a PK profile, with estimation of PK parameters such as plasma and saliva AUC and Cmax. The study shall be deemed complete when the 6th evaluable patient has completed therapy and the samples sent for PK analysis.

### **7.3 Statistical Methodology and Analysis Plan**

Statistical methodology: PK parameters for drug concentration in both saliva and plasma samples will be calculated. These PK parameters include area under the concentration curves to last collection time (AUCt), maximum measured concentration (Cmax) and time to maximum concentration (Tmax).

## **8 DATA AND SAFETY MONITORING PLAN (DSMP)**

### **8.1 Data and Safety Management Overview**

The Medical College of Wisconsin (MCW) Data Safety Monitoring Committee (DSMC) and the MCW Institutional Review Board (IRB) will approve protocol-specific DSM plans. A local, investigator-initiated trial will be required to be continuously monitored by the principal investigator of the study with safety and progress reports submitted to the DSMC.

The DSMP for this study will involve the following entities:

### **8.2 Study Team**

The study team minimally consists of the principal investigator, the clinical research coordinator, regulatory specialist, and the study biostatistician. While subjects are on study, the principal investigator will meet regularly with the research coordinator and the study biostatistician to review study status. This review will include but not be limited to reportable SAEs and UPIRSOs and an update of the ongoing study summary that describes study progress in terms of the study schema. The appropriateness of further subject enrollment and the specific intervention for a next subject enrollment is addressed. All meetings including attendance are documented.

### **8.3 Quality Assurance**

The MCWCC Clinical Trials Office provides ongoing quality assurance audits. This protocol was classified as high risk and will be reviewed internally by the MCW Cancer Center Clinical Trials Office Quality Assurance Staff according to the MCWCC Data and Safety Monitoring Plan and current version SOP, 6.5.2 Internal Quality Assurance Reviews.8.4 Clinical Trials Office

The MCWCC Clinical Trials Office (CTO) provides administrative assistance and support to the DSMC.

## 8.5 DSMC

The Medical College of Wisconsin Cancer Center places the highest priority on ensuring the safety of patients participating in clinical trials. Every cancer interventional trial conducted at MCW includes a plan for safety and data monitoring.

More information can be found related to the MCWCC Data and Safety Monitoring Plan at the MCWCC website ([Data and Safety Monitoring Plan](#)).

This study will be reviewed by the Medical College of Wisconsin Cancer Center Data and Safety Monitoring Committee (MCWCC DSMC). A summary of the MCWCC DSMC activities are as follows:

- Review the clinical trial for data integrity and safety
- Review all DSM reports
- Submit a summary of any recommendations related to study conduct
- Terminate the study if deemed unsafe for patients

A copy of the MCWCC Data and Safety Monitoring Plan and membership roster will be maintained in the study research file and updated as membership changes. The committee will review reports from the study PI twice annually (or more frequently if needed) and provide recommendations on trial continuation, suspension, or termination as necessary.

Any available DSMC letters will be submitted to the IRB of record as required.

## 9 REGULATORY COMPLIANCE, ETHICS, AND STUDY MANAGEMENT

This study will be conducted in accordance with the ethical principles that have their origin in the Declaration of Helsinki as stated in 21 CFR §312.120(c)(4); consistent with GCP and all applicable regulatory requirements.

### 9.1 Regulatory Compliance

This study will be conducted in compliance with:

- The protocol
- Federal regulations, as applicable, including: 21 CFR 50 (Protection of Human Subjects/Informed Consent); 21 CFR 56 (Institutional Review Boards) and 45 CFR 46 Subparts A (Common Rule), B (Pregnant Women, Human Fetuses and Neonates), C (Prisoners), and D (Children), GCP/ICH guidelines, and all applicable regulatory requirements. The IRB must comply with the regulations in 21 CFR §56 and applicable regulatory requirements.

## 9.2 Prestudy Documentation

Prior to implementing this protocol at MCWCC, the protocol, informed consent form, HIPAA authorization and any other information pertaining to participants must be approved by the MCW IRB.

The clinical investigation will not begin until the Investigator has received a letter from FDA stating that the study is exempt from IND requirements.

## 9.3 Institutional Review Board

The protocol, the proposed informed consent form and all forms of participant information related to the study (e.g., advertisements used to recruit participants) will be reviewed and approved by the MCW Institutional Review Board. Prior to obtaining MCW approval, the protocol must be approved by the Medical College of Wisconsin Cancer Center Scientific Review Committee. The initial protocol and all protocol amendments must be approved by the IRB prior to implementation.

### Informed Consent Process

Informed consent is a process that is initiated prior to the individual's agreeing to participate in the study and continues throughout the individual's study participation. Extensive discussion of risks and possible benefits of this therapy will be provided to the subjects and their families. Consent forms describing in detail the study interventions/products, study procedures and risks are given to the subject and written documentation of informed consent is required prior to starting intervention/administering study product.

Consent forms will be IRB-approved and the subject (and Legally Authorized Representative, if necessary) will be asked to read and review the document. Upon reviewing the document, the investigator will explain the research study to the subject and answer any questions that may arise. In accordance with 46 CR 46.111, the subject will sign and date the informed consent document prior to any procedures being done specifically for the study.

A witness should only sign when required, per FH/MCW IRB policy. If a witness signs the document when not required, the study staff should document in the legal medical record (or note to file) the relationship to the patient and why a witness signed. (i.e., "Although not required, the subject's spouse was present during the consenting process and signed as the witness." Or "Although not required, hospital staff was present for consenting process and signed as a witness.")

The subjects will have the opportunity to discuss the study with their surrogates or think about it prior to agreeing to participate. The subjects may withdraw consent at any time throughout the course of the trial.

A copy of the informed consent document will be given to the subjects for their records. The rights and welfare of the subjects will be protected by emphasizing to them that the quality of their medical care will not be adversely affected if they decline to participate in this study. If there are changes to the consent form, all revisions will be reviewed with study subject at the next appropriate opportunity. Patients that require reconsenting will be defined in the IRB approved amendment submission. The process for obtaining informed consent will again be performed. Study subjects will not be reconsented for continuing reviews. The MCWCC CTO will follow the MCW/FH IRB's policy for subjects who demonstrate limited English proficiency or limited literacy.

After the subject's visit in which the consent is signed, it is documented in the clinic chart that the consent has been signed and that all questions have been answered to the subject's satisfaction after adequate time for review of the consent. It is also documented that a copy of the consent is given to the subject. The original consent is kept with the subject's study file, and a copy of the consent is sent to the OCRICC office, which will then submit to HIM a copy of the signed consent to be scanned into EPIC, the legal medical record.

#### **9.4 Subject Confidentiality and Access to Source Documents/Data**

Subject confidentiality is strictly held in trust by the sponsor-investigator, participating investigators, and any staff, [and the sponsor(s) and their agents] (include bracketed portion if applicable). This confidentiality includes the clinical information relating to participating subjects, as well as any genetic or biological testing.

The study protocol, documentation, data, and all other information generated will be held in strict confidence. No information concerning the study, or the data will be released to any unauthorized third party without prior written approval of the principal investigator.

The conditions for maintaining confidentiality of the subjects' records are required for the life of the data. These rules apply equally to any and all MCWCC projects.

One risk of taking part in a research study is that more people will handle the personal health information collected for this study. The study team will make every effort to protect the information and keep it confidential, but it is possible that an unauthorized person might see it. Depending on the kind of information being collected, it might be used in a way that could embarrass the subject or affect his/her ability to get insurance.

While data are being collected and after all data have been collected but are still in the process of being analyzed, the subject's data/PHI are stored in the locked Clinical Research office in the Clinical Trials Office. Databases in which the study subject information is stored and accessed are password protected, allowing for limited access by authorized personnel only. Data/PHI kept in the Case Report Forms contain the study identifiers, subject initials, date of birth and date of service.

The principal investigator will allow access to all source data and documents for the purposes of monitoring, audits, IRB review, and regulatory inspections.

The study monitor/s or other authorized representatives of the principal investigator may inspect all documents and records required to be maintained by the investigator, including but not limited to, medical records (office, clinic, or hospital) and pharmacy records for the subjects in this study. The clinical study site will permit access to such records.

#### **9.5 Protection of Human Subjects**

##### **9.5.1 Protection from Unnecessary Harm**

Each clinical site is responsible for protecting all subjects involved in human experimentation. This is accomplished through the IRB mechanism and the informed consent process. The IRB reviews all proposed studies involving human experimentation and ensures that the subject's rights and welfare are protected and that the potential benefits and/or the importance of the knowledge to be gained outweigh the risks to the individual. The IRB also reviews the informed consent

document associated with each study in order to ensure that the consent document accurately and clearly communicates the nature of the research to be done and its associated risks and benefits.

### **9.5.2 Protection of Privacy**

As noted, patients will be informed of the extent to which their confidential health information generated from this study may be used for research purposes. Following this discussion, they will be asked to sign informed consent documents. The original signed document will become part of the patient's medical records, and each patient will receive a copy of the signed document.

### **9.5.3 Changes in the Protocol**

Once the protocol has been approved by the MCW IRB, any changes to the protocol must be documented in the form of an amendment. The amendment must be signed by the investigator and approved by IRB prior to implementation.

If it becomes necessary to alter the protocol to eliminate an immediate hazard to patients, an amendment may be implemented prior to IRB approval. In this circumstance, however, the Investigator must then notify the IRB in writing within five working days after implementation.

The IRB may provide, if applicable regulatory authority(ies) permit, expedited review, and approval/favorable opinion for minor change(s) in ongoing studies that have the approval /favorable opinion of the IRB. The investigator will submit all protocol modifications to the sponsor and the regulatory authority(ies) in accordance with the governing regulations.

Changes to the protocol may require approval from the sponsor.

Any departures from the protocol must be fully documented in the source documents.

## **9.6 Investigator Compliance**

The investigator will conduct the study in compliance with the protocol given approval/favorable opinion by the IRB and the appropriate regulatory authority(ies).

### Onsite Audits

Auditing is essential to ensure that research conducted at the Medical College of Wisconsin (MCW) Cancer Center is of the highest quality and meets MCW and regulatory agency standards.

Regulatory authorities, the IRB and/or sponsor may request access to all source documents, data capture records and other study documentation for on-site audit or inspection. Direct access to these documents must be guaranteed by the investigator, who must provide support at all times for these activities.

## **10 DATA HANDLING AND RECORD KEEPING**

### **10.1 Overview**

Every effort is made to uphold the integrity of the project, the research, the institution, and the researchers involved. Data collection guidelines and methodologies are carefully developed before the research begins. Investigators focus on the following to ensure data integrity: well-trained data collectors/recorders to ensure consistency and quality, well-designed data collection protocols and ongoing monitoring. In this way, study rigor and validity are maintained. Data is protected from physical damage as well as from tampering, loss, or theft. This project's data management is a multidisciplinary activity that includes investigators, research coordinators and nurses, data managers, support personnel, biostatisticians, and database programmers. Quality control will be applied to each stage of data handling to ensure that all data are reliable and have been processed correctly.

### **10.2 Data Management Responsibilities**

#### **Principal Investigator**

The principal investigator oversees the management of patient records/case report forms and ensures that a) complete and accurate data will be obtained and provided to the sponsor; b) patient records are maintained to include history, prescribed medication, and investigational product(s), measurements, exams, evaluations, and adverse events; c) corrections are applied to clinical research data according to principles of good research practice (i.e., single-line delete, date and initial). He or she will ensure that there is correlation between the case report forms and the source documents.

#### **Research Coordinator**

A research coordinator creates, collects, and organizes clinical trial documentation. He or she ensures that source documentation and data abstraction and entry are being done at protocol specified time points.

#### **Research Nurse/Medical Staff**

The research nurse and medical staff documents protocol-required care or assessment of the subject's outcomes, adverse events, and compliance to study procedures.

#### **Biostatistician**

The biostatistician may assist in CRF development (content and design), dataset specifications (annotation of CRFs and record layout) and validation.

### **10.3 Source Documents**

Source documents for clinical information (patient history, diagnosis, clinical and diagnostic test reports, etc.) are maintained in the patient's clinical file.

All source documents will be written following ALCOA standards:

ALCOA Attribute	Definition
Attributable	Clear who has documented the data.
Legible	Readable and signatures identifiable.
Contemporaneous	Documented in the correct time frame along with the flow of events. If a clinical observation cannot be entered when made, chronology should be recorded. Acceptable amount of delay should be defined and justified.
Original	Original, if not original should be exact copy; the first record made by the appropriate person. The investigator should have the original source document.
Accurate	Accurate, consistent and real representation of facts.
Enduring	Long-lasting and durable.
Available and accessible	Easily available for review by treating physicians and during audits/inspections. The documents should be retrievable in reasonable time.
Complete	Complete until that point in time.
Consistent	Demonstrate the required attributes consistently.
Credible	Based on real and reliable facts.
Corroborated	Data should be backed up by evidence.

#### **10.4 Case Report Forms**

The principal investigator and/or his/her designee will prepare and maintain adequate and accurate participant case histories with observations and data pertinent to the study. Study-specific Case Report Forms (CRFs) will document outcomes. All study data will be entered into OnCore® via standardized CRFs, in accordance with the study calendar, using single data entry with a secure access account. The clinical research coordinator will complete the CRFs as soon as possible upon completion of the study visit; the investigator will review and approve the completed CRFs.

The information collected on CRFs shall be identical to that appearing in original source documents. Source documents will be found in the patient's medical records maintained by MCWCC personnel. All source documentation should be kept in separate research folders for each patient.

In accordance with federal regulations, the investigator is responsible for the accuracy and authenticity of all clinical and laboratory data entered onto CRFs. The principal investigator will approve all completed CRFs to attest that the information contained on the CRFs is true and accurate.

All source documentation and data will be available for review/monitoring by the MCWCC DSMC and regulatory agencies.

#### **10.5 Study Record Retention**

The principal investigator is required to maintain adequate records.

The principal investigator is required to prepare and maintain adequate and accurate case histories that record all observations and other data pertinent to the investigation.

Case histories include the case report forms and supporting data including, for example, signed and dated consent forms and medical records including, for example, progress notes of the physician, the individual's hospital chart(s), and the nurses' notes. The case history for each individual shall document that informed consent was obtained prior to participation in the study.

Study documentation includes all CRFs, data correction forms or queries, source documents, sponsor-investigator correspondence, monitoring logs/letters, and regulatory documents (e.g., protocol and amendments, IRB correspondence and approval, signed patient consent forms).

Source documents include all recordings of observations or notations of clinical activities and all reports and records necessary for the evaluation and reconstruction of the clinical research study.

## APPENDIX 1. PERFORMANCE STATUS CRITERIA

ECOG Performance Status Scale		Karnofsky Performance Scale	
Grade	Descriptions	Percent	Description
0	Normal activity Fully active, able to carry on all pre-disease performance without restriction	100	Normal, no complaints, no evidence of disease
		90	Able to carry on normal activity; minor signs or symptoms of disease
1	Symptoms, but ambulatory Restricted in physically strenuous activity, but ambulatory and able to carry out work of a light or sedentary nature (e.g., light housework, office work)	80	Normal activity with effort; some signs or symptoms of disease
		70	Cares for self, unable to carry on normal activity or to do active work
2	In bed < 50% of the time Ambulatory and capable of all self-care, but unable to carry out any work activities Up and about more than 50% of waking hours	60	Requires occasional assistance, but is able to care for most of his/her needs
		50	Requires considerable assistance and frequent medical care
3	In bed > 50% of the time Capable of only limited self-care, confined to bed or chair more than 50% of waking hours	40	Disabled, requires special care and assistance
		30	Severely disabled, hospitalization indicated Death not imminent
4	100% bedridden Completely disabled Cannot carry on any self-care Totally confined to bed or chair	20	Very sick, hospitalization indicated Death not imminent
		10	Moribund, fatal processes progressing rapidly
5	Dead	0	Dead

## **APPENDIX 2. STUDY DIARY**

Participants will complete study diary to track compliance, saliva specimen collection, and daily symptom documentation. A paper study diary will be provided to each subject at screening to record the following information:

1. Study Agent administration date and time
2. Time of saliva sample collection
3. Side effects and/or any new symptoms

Patients will be trained on use of the diary. The diary will be provided in paper format and remain with the patient for the duration of the study. The study coordinator will review the diary for completeness and request missing information periodically and in a timely manner. Side effects/symptoms recorded in the diary will be reported as AEs according to the investigator's discretion and clinical judgment. The subject diary will serve as a source record and remain at the study site after the subject completes the study.

Study coordinator will contact patients twice weekly for compliance assessment and reminders for protocol procedures. At the end of the course of therapy patients will be asked to return the storage specimens to the study coordinator. Patients will be given a Styrofoam transportation container with freeze packs for this purpose. Patient will complete study diary with all relevant information and will submit the diary to study coordinator on the day of surgery.

## STUDY DIARY PATIENT INSTRUCTIONS:

1. Study coordinator will provide you specific instruction on how to complete the diary
2. Record the date, when you took ATB, and when you took them. Record dose as soon as you take them; do not batch entries together at a later time.
3. Record the time of saliva sample collection. Collect saliva sample even if you miss any dose.
4. If you have any comments or notice any side effects, please record them in the Comments/Symptoms. If you make a mistake while you write, please cross it out with one line, put your initials next to it, and then write the corrected information next to your initials
5. If you miss a dose of ATB, you should take it as soon as possible, as long as it is on the same day. Do not take an extra dose of ATB on the next day or any subsequent days to make it up for the missed dose.
6. Please return this diary to the study coordinator after study completion

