### **ATB Dose and Schedule**

ATB has been administered in clinical studies for upper aerodigestive disease prevention in wide ranges of agent dose and schedule, summarized in Table 2 below. Tablet strength in all of these studies was 300 mg. The dose range used in clinical trials was from 2400 mg/d to 4800 mg/d. The duration of therapy ranged from two months to five years.

Study description	Dose/schedule
SATCM (State Administration of Traditional Chinese Medicine) Multicenter Trial, 380 hospitals, 24,275 pts	8 tabs BID (4,800 mg/d) x2 months ON, 1 week OFF= one cycle Duration 2 years
Oral Leukoplakia n=150 ATB; control =148	8 tabs BID (4,800 mg/d) x 2 months
Oral Leukoplakia. n=59 ATB; n=53 placebo (8)	4 tabs TID (3,600 mg/d)
Henan province 1983 Esoph dysplasia, ZSP N=744 agent; n=777 placebo	8 tabs QD (2,400 mg/d) x 5 years
1984 Hebei Province N=300 randomized to ZSP and n=149 control	8 tabs BID (4,800/d) x 6 months

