**Table 2 Summary of clinical trials illustrating dose and schedule of ATB.**

In the current trial, the dose of ATB is in the mid-range (3,600 mg/d), but significantly shorter duration, compared to other ATB studies.

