## 5 TREATMENT PLAN

### 5.1 ATB Administration

ATB will be administered on an outpatient basis. ATB will be administered at a dose of 1,200 mg three times per day (roughly spaced every eight hours) as has been studied for ATB in human oral leukoplakia trials and in esophageal cancer prevention trials. ATB may be taken with or without food.

Regimen Description					
Study agent	Premedication; precautions	Dose	Route	Schedule	Duration
ATB	None	1,200 mg, Three times a day	Oral	Daily	7-28 days a
a. Total duration depends upon scheduling of surgery. ATB administration must not exceed 28 days.					

- There will only be ONE ATB dose on day 1. Dose on Day 2 must be delayed until completion of PK specimen (blood and saliva) collection.
- Patient must submit completed study dairy to the study coordinator.

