## 5.10 Monitoring Subject Compliance

ATB will be administered or dispensed only to eligible patients under the supervision of the investigator or trained study staff or identified sub investigator(s). The appropriate study personnel will maintain records of study agent receipt and dispensing. Comprehensive instructions will be provided to the patient to ensure compliance with dosing procedures.

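### The missed-dose rule in the patient diary sets no minimum interval and no limit per intake, so on a three-times-daily regimen it leaves room for up to 12 tablets (3,600 mg) at once

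*Combined protocol and SAP*

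**What the plan says.** Section 5.1 sets the regimen: "ATB will be administered at a dose of 1,200 mg three times per day (roughly spaced every eight hours". Day 1 is an exception, with a single dose. Earlier ATB trials used 300 mg tablets (section 1.1, ATB Dose and Schedule), so one dose is four tablets. Section 5.7 allows reduction to 900 mg and then 600 mg three times daily.

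The missed-dose rule is in the diary instructions in Appendix 2, item 5: "If you miss a dose of ATB, you should take it as soon as possible, as long as it is on the same day". It continues: "Do not take an extra dose of ATB on the next day or any subsequent days to make it up for the missed dose".

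Section 5.10 adds: "Comprehensive instructions will be provided to the patient to ensure compliance with dosing procedures". The content of those instructions is not given. The bottle-label template in section 5.2 has no wording on spacing or missed doses. The diary has separate rows for Doses 1, 2 and 3, and it records "Study Agent administration date and time".

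On earlier exposure, section 1.1 states: "The dose range used in clinical trials was from 2400 mg/d to 4800 mg/d". Table 2 includes "8 tabs BID (4,800 mg/d) x2 months" in oral leukoplakia and 8 tablets once daily for five years in Henan.

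**The concern.** A same-day catch-up rule suits a once-daily drug, because the next dose falls on another day. On a three-times-daily drug the next dose usually falls on the same day. A patient who remembers Dose 1 when Dose 2 is due can follow item 5 to the letter and take both. One who remembers Doses 1 and 2 only at Dose 3 can take all three. The only extra dose that item 5 forbids is one on a later day.

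What is at stake is the size of a single intake, not the daily amount. It matters most in two situations: the 12-tablet intake, which is larger than any listed in Table 2, and the patient whose dose was lowered for toxicity, in whom catching up can briefly undo the reduction.

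**Working it through.** **Planned dose.** 3 × 1,200 mg = 3,600 mg/d, which agrees with the statement under Table 2: "In the current trial, the dose of ATB is in the mid-range (3,600 mg/d". Tablets per dose: 1,200 / 300 = 4.

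**Single intake when k scheduled doses are taken together (k × dose).**

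| Dose level | One dose | Two together | Three together |
|---|---|---|---|
| 0 (1,200 mg) | 1,200 mg | 2,400 mg (8 tablets) | 3,600 mg (12 tablets) |
| −1 (900 mg) | 900 mg | 1,800 mg | 2,700 mg |
| −2 (600 mg) | 600 mg | 1,200 mg | 1,800 mg |

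The largest single intake in Table 2 is 8 × 300 = 2,400 mg. The full-dose triple is 3,600 / 2,400 = 1.5 times that and 3,600 / 1,200 = 3 times the planned dose. The double at level −1 is 1,800 / 1,200 = 1.5 times the dose the patient was reduced from. At level −2 a double equals the original single dose. In every case the day's total stays at or below plan.

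**How often the situation could arise.** The documents give no miss rate. Assume each dose is missed independently with probability p = 2%, 5% or 10%. Only Doses 1 and 2 can be combined with a later dose on the same day, and three-dose days number 6 in a 7-day course and 27 in a 28-day course.

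- At least one miss of Dose 1 or 2: 1 − (1 − p)^12 = 22%, 46%, 72% (7 days); 1 − (1 − p)^54 = 66%, 94%, 99.7% (28 days).
- Both missed on some day: 1 − (1 − p²)^6 = 0.2%, 1.5%, 5.9% (7 days); 1 − (1 − p²)^27 = 1.1%, 6.5%, 24% (28 days).

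These are chances of the opportunity, not of combined intake, which also requires that the miss be remembered only when a later dose is due. Misses that cluster within a day would make the second set larger, so it is not a general upper bound on triple intake.

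**Peak concentration.** The documents contain no human pharmacokinetic values. Assume a one-compartment model with absorption rate 1.5/h, half-life 1.5 to 12 h, doses at 07:00, 15:00 and 23:00 for six days, and the miss on day six. The comparator is 2,400 mg twice daily at steady state, as in Table 2.

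| Peak relative to planned regimen | 1.5 h | 3 h | 6 h | 12 h |
|---|---|---|---|---|
| Double intake at 15:00 | 1.93 | 1.66 | 1.32 | 1.11 |
| Triple intake at 23:00 | 2.89 | 2.45 | 1.80 | 1.32 |
| 2,400 mg twice daily | 1.94 | 1.76 | 1.58 | 1.46 |
| Triple ÷ twice-daily precedent | 1.49 | 1.39 | 1.14 | 0.90 |
| Dose 1 skipped | 1.00 | 0.98 | 0.90 | 0.85 |
| Dose 1 taken at 11:00 (4 h before Dose 2) | 1.19 | 1.24 | 1.15 | 1.06 |

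The full-dose double peaks below the twice-daily precedent at every half-life. The triple exceeds it except at 12 h.

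**Later saliva on the same day.** Modelled 18:00 concentration relative to plan, in the same half-life order: double 1.95, 1.70, 1.36, 1.13; skipped 0.97, 0.86, 0.76, 0.77.

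**The case against.** Item 5 does not tell anyone to combine doses. Its direction to act early tends to separate the missed dose from the next one. Section 5.1 gives an eight-hour spacing, the diary is laid out for three separate intakes, and the coordinator contacts patients twice weekly. The instructions promised in section 5.10 may cover the point. All of this is fair, but none of the visible text gives a missed-dose interval or a cap. Item 5 is the written rule that the patient keeps at home.

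The more common case, 2,400 mg at once, was routine in earlier trials, including 8 tablets twice daily in the 24,275-patient multicentre study. The Hebei study at that dose reported no toxicity. This stands: a reader might infer that any doubled dose is a hazard, and Table 2 does not support that at full dose.

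The factor of 1.5 for the triple is a ratio of milligrams. In the model the peak ratio to precedent is 0.90 to 1.49, so higher exposure is not assured. A triple also needs two misses on one day and a patient willing to swallow 12 tablets. This stands too.

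A reader might also infer that the rule damages the pharmacokinetic results. It does not touch the Day 1 profile, which follows a single dose. From Day 2 a missed dose disturbs later saliva samples under either rule. At a 12 h half-life, skipping departs further from plan at 18:00 (0.77) than doubling does (1.13). The remedy has no pharmacokinetic advantage to claim.

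The reduced-dose case is narrow: 1,800 mg is below the 2,400 mg precedent, the day's total stays at 2,700 mg, and reductions should be uncommon in a course of 7 to 28 days. But that precedent does not speak for a patient who has already shown toxicity at 1,200 mg per dose.

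**Conclusion.** The gap in the printed rule is real and minor. At full dose it permits, by silence, up to 3,600 mg at once, 1.5 times in mg the largest single intake in Table 2. At dose level −1 it permits 1,800 mg, 1.5 times the dose the patient was reduced from. The safety gain from closing it is confined to these two cases. The daily total, the Day 1 profile and the primary endpoint are not affected.

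The intake sizes follow directly from the stated regimen. The frequencies and peak ratios do not: they rest on assumed miss rates, independence between misses, and an assumed one-compartment model, and should be read as illustration. The documents do not show that any patient would be harmed, or that patients are left without other guidance.

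**What to change.** Replace item 5 with wording such as:

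*If you miss a dose, take it only if your next dose is not close (for example, at least about 4 hours away). Otherwise skip it. Never take more than one dose (4 tablets, or your assigned reduced number) at a time, and do not make up a missed dose on a later day.*

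The investigator should set the interval; 4 hours is only an example. The largest single intake then becomes 1,200, 900 or 600 mg by dose level. The instructions under section 5.10 should say the same. Saliva samples from Day 2 onward should be interpreted by the dose times already recorded in the diary.

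The cost is one revised item and an occasional skipped dose. One skipped dose at full level gives 3,600 − 1,200 = 2,400 mg that day, still within the earlier range of 2,400 to 4,800 mg/d. Saliva levels later that day would be lower (modelled 18:00 value 0.76 to 0.97 of plan).
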